4.3 Withdrawal of Subjects

It is the right and duty of the Investigator to discontinue the study participation of a subject when the subject's health or well-being is threatened by continuation in the study. Such subjects should be withdrawn from the study.

The following are circumstances that would result in the subject's discontinuation from the study:

- the subject experiences a serious adverse event rendering them unable to continue study participation;
- the subject is unable to physically or mentally tolerate the use of the test medication;
- an exclusion criterion becomes apparent at any time during the study; or
- the subject voluntarily withdraws.

In the event of premature discontinuation from the study, the Investigator should determine the primary reason for discontinuation. A subject who is withdrawn from the study prior to initiation of treatment may be replaced.

WIN2023 (v.06feb2023) Page 5 of 14

5 TREATMENT OF SUBJECTS AND FOLLOW-UP

5.1 **Study Procedures**

5.1.1 Assessment Schedule

	Screening	Baseline	Follow-up Visits	
	Visit 0 -30 days	Visit 1 WK 0	Visit 2, 3, 4 Wk 4, 8, 12,	Visit 5 Wk 16
ICF/HIPAA	Х			
Subject Demographics/Medical Hx/Height	Х			
Weight	Х			Χ
Inclusion/Exclusion Criteria	Х	Х		
Vital Signs	Х	Х	Х	Х
Urine Pregnancy Test	X ¹	Х	X ¹	X1
Acne IGA Lesion Counts² Tolerability³	X	х	x	Х
Study Medication; Dispense Collect		D	C D	С
DLQI		Х	х	Х
Concomitant medication/Treatment	Х	Х	Х	Х
Adverse Events	Х	X	Х	Х

- 1 Female subjects of childbearing potential.
- Lesion Counts: papules, pustules, nodules, open/closed comedones
 Peeling, erythema, dryness, oiliness, burning, pruritus

5.1.2 Visit 0 (Screening Visit)

- Informed Consent/HIPAA
- Urine Pregnancy Test (if applicable)
- Subject Demographics/Medical History/Height
- Weight
- Vital Signs
- Concomitant Medication/Treatment
- Assessments
 - Acne IGA
 - Lesion Counts
 - Tolerability
- Inclusion/Exclusion Criteria

Baseline (visit 1)

Urine Pregnancy Test (if applicable)

WIN2023 (v.06feb2023) Page 6 of 14

- Subject Demographics/Medical History
- Weight/Height
- Vital Signs
- Concomitant Medication/Treatment
- Assessments
 - Acne IGA
 - Lesion Counts
 - Tolerability
- Inclusion/Exclusion Criteria
- Dispense Study medication
- DLQI
- Instruct regarding application procedures

5.1.3 Visits 2, 3, 4 (Weeks 4, 8, 12 ± 3 days)

- Concomitant Medication/Treatment
- Urine Pregnancy Test (if applicable)
- Adverse Events
- Vital Signs
- Collect Study Medication
- DLQI
- Assessments
 - Acne IGA
 - Lesion Counts
 - Tolerability

5.1.4 Visit 5 (Week 16; ± 5 days)

- Urine Pregnancy Test (if applicable)
- Concomitant Medication/Treatment
- Adverse Events
- Vital Signs
- Weight
- DLQI
- Assessments
 - Acne IGA
 - Lesion Counts
 - Tolerability

5.2 Study Treatment

5.2.1 Details of Study Treatment

Apply a thin layer of DUAC Gel to the face once daily, in the evening. (2) ● Not for oral, ophthalmic, or intravaginal use. (2)

WIN2023 (v.06feb2023) Page 7 of 14

WINLEVI cream 1% is supplied in an epoxy-lined aluminum blind-end tube with a polypropylene cap closure: NDC 47335-994-36 60-gram tube

5.2.2 Storage and Handling

DUAC (clindamycin phosphate and benzoyl peroxide) Gel, 1.2%/5% is a fixed combination product with two active ingredients in a white to slightly yellow, opaque, aqueous gel formulation. Clindamycin phosphate is a water soluble ester of the semi-synthetic antibiotic produced by a 7(S)-chloro-substitution of the 7(R)-hydroxyl group of the parent antibiotic lincomycin. Clindamycin phosphate is C18H34ClN2O8PS. The structural formula for clindamycin phosphate is represented below: 5 Reference ID: 3428618 CH3 Cl N H H H N CH3 H H OH 3C O O H OH SC H 3 O OH P HO O Clindamycin phosphate has a molecular weight of 504.97 and its chemical name is methyl 7-chloro-6,7,8-trideoxy-6-(1-methyl-trans-4-propyl-L-2-pyrrolidinecarboxamido)-1-thioL-threo-α-D-galacto-octopyranoside 2-(dihydrogen phosphate). Benzoyl peroxide is C14H10O4. It has the following structural formula: Benzoyl peroxide has a molecular weight of 242.23. Each gram of DUAC Gel contains 10 mg (1%) clindamycin, as clindamycin phosphate, and 50 mg (5%) benzoyl peroxide in a base consisting of carbomer homopolymer (type C), dimethicone, disodium lauryl sulfosuccinate, edetate disodium, glycerin, methylparaben, poloxamer 182, purified water, silicon dioxide, and sodium hydroxide.

WINLEVI (clascoterone) cream contains clascoterone, an androgen receptor inhibitor, in a cream base for topical dermatologic use. WINLEVI cream is a white to almost white cream. Chemically, clascoterone is cortexolone- 17α propionate. Clascoterone is a white to almost white powder, practically insoluble in water. The compound has the empirical formula C24H34O5 and molecular weight of 402.5 g/mol. The structural formula is shown below. Each gram of WINLEVI cream 1% contains 10 mg of clascoterone in a cream base of cetyl alcohol, citric acid monohydrate, edetate disodium, mineral oil, mono- and di-glycerides, polysorbate 80, propylene glycol, purified water, and vitamin E.

5.2.3 Dispensation and Dosage Schedule

Apply a thin layer of DUAC Gel to the face once daily, in the evening. (2) • Not for oral, ophthalmic, or intravaginal use. (2)

Winlevi Cream• Apply a thin layer (approximately 1 gram) to affected area twice daily (morning and evening). Avoid contact with eyes, mouth, and mucous membranes. (2) • Not for ophthalmic, oral or vaginal use. (2)

WIN2023 (v.06feb2023) Page 8 of 14

5.2.4 Treatment Assignment

The study medication will be administered only to eligible subjects as defined by the Study Protocol. All subjects who have signed an ICF will receive a 2-digit subject number, starting at 01. This subject number will be used to identify the subject throughout the study. Subjects withdrawn from the study will retain their subject number. New subjects will be allotted a new subject number.

5.2.5 Blinding, Packaging, and Labeling

Commercially available and labeled medications will be used. Medications will be dispensed in an open-label fashion.

5.2.6 Supplies and Accountability

The Investigator or pharmacist will inventory and acknowledge receipt of all shipments of study medication. All study medication must be kept in a locked area with access restricted to designated study personnel. The study medication must be stored in accordance with the instructions provided with the shipment. The Investigator or pharmacist will also keep accurate records of the quantities of study medication dispensed and returned by each subject.

5.2.7 Treatment Compliance

Subject compliance to study treatment regimen will be assessed at each visit; study personnel will ask each subject whether they missed any applications of study medication since the previous visit.

5.3 Concomitant Medication/Treatment

Please see Supplement I for a listing of prohibited medications. Necessary therapies that will not interfere with the response to treatment may be provided at the discretion of the Investigator. The use of any concurrent medication, prescription or over-the-counter drug, is to be recorded in the CRF along with the reason the medication was taken.

5.4 Summary of known and potential risks

5.5 Summary of Benefits

There may be certain direct benefits derived from participating in this study. Such benefits include temporary, partial or complete, clearance of your acne lesions; however, it is possible that you receive no benefit. The results of this study may be useful in the development of a new therapy for others with similar conditions to yours.

WIN2023 (v.06feb2023) Page 9 of 14

6 STUDY ASSESSMENTS

6.1 Primary Endpoint

The primary endpoint of this study is the percent of patients who achieve clear or almost clear on IGA at week 16.

6.1.1 Acne IGA

The Investigator will evaluate global acne severity using the following Investigator Global Assessment scale:

Score	Description
0 = Clear Skin	Clear Skin; no inflammatory or non-inflammatory lesions
1 = Almost Clear	Almost clear; rare non-inflammatory lesions with no more than one small inflammatory lesion
2 = Mild Severity	Mild severity; greater than Grade 1; some non-inflammatory lesions with no more than a few inflammatory lesions (papules/pustules only, no nodular lesions)
3 = Moderate Severity	Moderate severity; greater than Grade 2; some to many non-inflammatory lesions and may have some inflammatory lesions, but no more than one small nodular lesion
4 = Severe	Severe; greater than Grade 3; some to many non-inflammatory and inflammatory lesions, but no more than a few nodular lesions
5 = Very Severe	Very Severe; greater than Grade 4; many non-inflammatory and/or inflammatory lesions with some or many nodular lesions

6.2 Secondary Endpoints

- 1. Percent of total lesion reduction at week 16 compared to baseline
- 2. Percent of inflammatory lesion reduction at week 16 compared to baseline
- 3. Percent of non-inflammatory lesion reduction at week 16 compared to

baseline.

4. Tolerability measures such as, erythema, scaling, dryness, oiliness, burning/stinging and pruritus.

6.2.1 Tolerability

The Investigator will grade the current severity of erythema (disease related and/or related to IP use), dryness, peeling, and oiliness as per the following:

Score Erythema		Dryness	Peeling	Oiliness
0 = Absent	No redness	None	Smooth	Normal
1 = Trace	Faint red or pink coloration, barely perceptible	Barely perceptible dryness by palpation with no accentuation of skin markings, skin desquamation (flakes) or fissure formation	Fine peeling, barely perceptible	Mild and localized
2 = Mild	Light red or pink coloration	Easily perceptible dryness by palpation with accentuation of skin markings but no skin desquamation (flakes) or fissure formation	Slight peeling	Mild and diffuse
3 = Moderate	Medium red coloration	Easily noted dryness with accentuation of skin markings and skin desquamation (small flakes) but no fissure formation	Definitely noticeable peeling	Moderate and diffuse
4 = Severe	Beet red coloration	Easily noted dryness with accentuation of skin markings, skin desquamation (large	Extensive peeling	Prominent and dense

WIN2023 (v.06feb2023) Page 10 of 14

The **Investigator** will **interview the subject** to determine the current severity of pruritus and burning/stinging; these symptoms will be graded as per the following:

Score	Description	
0 = Absent	Normal, no discomfort	
1 = Trace	An awareness, but no discomfort and no intervention required	
2 = Mild	Noticeable discomfort causing intermittent awareness	
3 = Moderate	Noticeable discomfort causing continuous awareness	
4 = Marked	Definite discomfort causing continuous awareness interfering occasionally with normal daily activities	
5 = Severe	Definite, continuous discomfort interfering with normal daily activities	

6.2.3 Vital Signs

The Investigator will measure vital signs (SBP, DBP, HR, T°) and weight as per his standard of care.

7 ASSESSMENTS OF SAFETY

7.1 Safety Assessments

Throughout the study, subjects will be monitored for signs and symptoms of adverse events. An *adverse event* is any pathological or unintended change in the structure, function or chemistry of the body that occurs during the study, irrespective of causality, including any illness, injury, toxicity, sensitivity, or sudden death. The condition must either not be present pre-study or must worsen in either intensity or frequency during the study.

A serious adverse event is any untoward medical occurrence, that, at any dose:

- results in death;
- is life-threatening;
- requires in-patient hospitalization or prolongation of existing hospitalization;
- results in persistent or significant disability/incapacity;
- is a congenital anomaly/birth defect; or
- is an important medical event.

An *unexpected adverse event* is any treatment-related adverse event, which is not identified in nature, severity, or frequency in current literature on the test product.

7.2 Reporting Requirements

7.2.1 Serious and/or Unexpected Adverse Events

Any serious or treatment-related unexpected adverse event occurring in this study must be reported to the IRB within its stipulated reporting timelines.

7.2.2 Adverse Event Reporting

All adverse events must be recorded by the Investigator into the CRF. The Investigator will be required to describe the adverse event, onset and stop date, severity, the course of action taken, if any, as well as any pertinent data necessary to allow a complete evaluation of the adverse event. For serious adverse events, an additional report (SAE report) must be completed.

WIN2023 (v.06feb2023) Page 11 of 14

7.2.3 Follow-up and Final Reports

Subjects who have had a serious adverse event must be followed clinically until all parameters, including laboratory values (if applicable), have either returned to normal or are otherwise explained.

If death was the outcome of the event on the initial SAE Report, a Follow-up/Final Report, including autopsy report, when performed, must be completed.

8 STATISTICS

8.1 Sample Size Justification

A total of 20 subjects will be entered into the study. This is a pilot study and a formal justification for the sample size is not provided. The data from this study will provide important data for determining any trends regarding the safety and efficacy of study medication.

8.2 Analyses

Statistical analyses will be conducted on an intent-to-treat basis (i.e., all enrolled subjects will be included in the analyses). All statistical tests will be two-sided and interpreted at a 5% significance level. Descriptive statistics (i.e., mean, standard deviation, etc.) will be provided for all continuous variables and frequencies for all categorical variables collected in this study. These will be presented by treatment group. Summary tables will be used to present patient population characteristics at Baseline; data from the study questionnaires will be included. The incidence and severity of adverse and/or unexpected events will be tabulated and a complete listing of all reports of adverse and/or unexpected events will be presented.

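### Section 4.3 takes subjects who could still be assessed out of the study, so week-16 values are lost that the all-enrolled analysis in Section 8.2 needs

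*Combined protocol and SAP*

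**What the plan says.** Section 8.2 sets the analysis population: "Statistical analyses will be conducted on an intent-to-treat basis (i.e., all enrolled subjects will be included in the analyses". It then promises summaries only: "Descriptive statistics (i.e., mean, standard deviation, etc.) will be provided for all continuous variables and frequencies for all categorical variables collected in this study". Neither that section nor any other says how a missing value is handled.

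Section 6.1 defines the primary result: "The primary endpoint of this study is the percent of patients who achieve clear or almost clear on IGA at week 16". Section 6.2 adds percent reductions in total, inflammatory and non-inflammatory lesions at week 16. (Section 2 places the total-lesion objective at week 12; the point below applies at either visit.)

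Section 4.3 opens its list with "The following are circumstances that would result in the subject's discontinuation from the study". The list has four entries. The first is a serious adverse event that prevents further participation. The second is intolerance, worded as "the subject is unable to physically or mentally tolerate the use of the test medication". The third concerns eligibility and applies when "an exclusion criterion becomes apparent at any time during the study". The fourth is the subject's own decision, where "the subject voluntarily withdraws". After premature discontinuation, "the Investigator should determine the primary reason for discontinuation"; no final IGA or lesion count is requested. Subjects withdrawn before treatment starts may be replaced.

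Sections 5.1.1 to 5.1.4 schedule screening, baseline and weeks 4, 8, 12 and 16, with no early-termination visit. Section 7.2.3 requires clinical follow-up after a serious adverse event, but no efficacy assessment.

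**The concern.** The analysis promise and the withdrawal rule work against each other. An intent-to-treat analysis needs outcomes from subjects who stop treatment. Section 4.3 treats stopping for intolerance, or because an exclusion criterion comes to light, as leaving the study, so those outcomes are never collected even when the subject is willing and able to attend.

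The week-16 IGA percentage is the main result of a small, open-label, single-regimen pilot. If values are missing and no rule is written, the handling can be chosen after the results are known. A frequency table of available week-16 values would give a completers' rate under an intent-to-treat label. For the lesion reductions, the promised means would silently become completers' means.

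**Working it through.** **Inputs.** From the documents: planned size 20 (Section 8.1) or 10 (Section 1.2), with a formal justification expressly not given, so there is no sample size calculation to reproduce. The documents give no dropout rate and no response rate. All counts of missing subjects and responders below are assumptions.

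**Step 1: which week-16 values are lost by rule?** Of the four reasons in Section 4.3, voluntary withdrawal and a serious adverse event that prevents participation end follow-up by their nature. Intolerance and a late-found exclusion criterion do not; there the loss comes from the rule. No early-termination visit or later follow-up collects the value.

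**Step 2: primary endpoint.** Let n be enrolled, m missing at week 16, and r observed responders.

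- Missing counted as not clear/almost clear: r/n
- Observed cases: r/(n − m)
- Relation: r/n = [r/(n − m)] × (1 − m/n)
- Range of the true all-enrolled rate: r/n to (r + m)/n, a width of m/n

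With n = 20 and r = 6 (assumed):

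| m | Observed cases | Missing = non-response | Upper bound |
|---|---|---|---|
| 1 | 6/19 = 31.6% | 30.0% | 7/20 = 35.0% |
| 2 | 6/18 = 33.3% | 30.0% | 8/20 = 40.0% |
| 4 | 6/16 = 37.5% | 30.0% | 10/20 = 50.0% |

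At m = 4 the two rules differ by 37.5 − 30.0 = 7.5 points. The exact (Clopper-Pearson) 95% intervals are 15.2% to 64.6% for 6/16 and 11.9% to 54.3% for 6/20, so the gap is well inside sampling error. Because the true all-enrolled rate could lie anywhere from 30.0% to 50.0%, the observed-case rate could be too high or too low. Each missing subject widens the range by 1/n: 5 points at n = 20, 10 points at n = 10.

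**Step 3: lesion reductions.** The all-enrolled mean is (1 − m/n) × observed mean + (m/n) × mean of the missing. With an assumed observed mean of 60% and 20% missing, it is 48.0% + 0.20 × (mean of the missing). If the missing had 0% change it is 48.0%; if they matched the completers it is 60.0%. The second term is unknown, so the mean cannot be computed without a week-16 value or a stated method.

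**Step 4: will it arise?** If each subject independently has a chance d of having no week-16 value, P(at least one missing) = 1 − (1 − d)^n. For d = 5%, 10% and 20% (assumed) this is 40.1%, 65.1% and 89.3% at n = 10, and 64.2%, 87.8% and 98.8% at n = 20.

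**Step 5: who is enrolled?** Section 5.2.4 numbers everyone who signs consent, and Section 4.3 allows replacement before treatment. If enrolled means consented, untreated subjects would enter the denominator as failures. Assumed example: 6 responders among 20 treated is 30.0%; with 4 untreated added it is 6/24 = 25.0%.

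**The case against.** The strongest reply is that the primary endpoint is nearly settled. Section 6.1 counts patients who achieve success and Section 8.2 includes everyone enrolled, so a subject with no week-16 success sits in the denominator and not in the numerator. That largely stands: a reader might infer that the primary denominator is undefined, and the text does not support that. What remains is that the rule is implicit and that enrolled is not defined. The reply does not reach the lesion means.

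A reader might also infer that every reason in Section 4.3 discards recoverable data. Two of the four end participation by definition, so extra visits would help mainly with the other two.

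Nor do the documents show that the reported rate would be inflated. They give no dropout or response rate, and nothing shows that leavers respond less. Safety data are not lost wholesale either: adverse events and tolerability grades recorded before withdrawal remain.

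Entering 0% change for a missing lesion count would be a debatable choice, since counts at weeks 4, 8 and 12 are already collected and would be ignored. That stands, and it shapes the fix.

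Finally, this is a pilot with no comparator, named test or success threshold, so no decision rule turns on the choice. That limits the weight of the point. It does not remove the mismatch between withdrawal rule and analysis population, which is cheap to repair.

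**Conclusion.** The point holds, and the sponsor should act on it. Section 4.3, with no early-termination assessment, loses week-16 values from subjects who could still be seen, while Section 8.2 promises to analyse everyone enrolled. The primary denominator is implied but not stated; the all-enrolled lesion means cannot be computed as planned once a week-16 count is missing.

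The consequence is modest and rests on assumed counts: the 7.5-point difference in the illustration is smaller than the sampling error, and neither the size nor the direction of any bias can be derived from the documents.

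The stated sample size is a plain contradiction (10 in Section 1.2, 20 in Section 8.1). A reader might take it to fix the denominator of the response rate. It does not, because the number actually enrolled does; it matters here because each missing subject weighs twice as much at 10.

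The documents also disagree on medication supply. Section 3 gives 12 weeks of treatment and 4 of safety follow-up. The Section 5.1.1 table, as extracted, shows collection and dispensing in the merged week 4, 8 and 12 column and collection at week 16. Section 5.1.3 lists collection only, and Section 5.1.4 none. These places must be reconciled, but that is a separate finding.

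**What to change.** The changes concern data collection and analysis only; the reasons for stopping medication and the investigator's discretion stay as they are.

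1. **Section 4.3 and Section 5.1.** Ask subjects who stop early to attend the remaining scheduled visits for IGA, lesion counts, tolerability and adverse events, unless they withdraw consent or cannot continue.
2. **Section 8.2, primary endpoint.** First define enrolled so that consented-but-untreated or replaced subjects are not counted as non-responders. Then state that a missing week-16 IGA counts as not clear/almost clear. Beside it, show the observed-case rate, the number missing and the reasons, which Section 4.3 already has the investigator determine.
3. **Section 8.2, lesion reductions.** Report the observed mean with its n at each visit, and pre-state one sensitivity analysis that uses the week 4, 8 and 12 counts.
4. **Sections 1.2 and 8.1.** Reconcile 10 and 20 as an error in the stated sample size.

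The cost is a few sentences of protocol text and a few visits by subjects off drug. The main response rate may come out lower, and it will be too low if leavers would have responded, which is why the observed-case rate stays beside it.

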8.3 Interim Analyses

No interim analyses will be conducted.

9 RESPONSIBILITIES OF THE INVESTIGATOR

9.1 Good Clinical Practice

Investigators must adhere to the procedures outlined in this Study Protocol. The procedures set out in this study protocol, pertaining to the conduct, evaluation, and documentation of this study, are designed to ensure that the Investigators and CRO abide by GCP as described in the ICH Guidelines Topic E6: "Guideline for Good Clinical Practice." Compliance with these regulations also constitutes compliance with the ethical principles described in the current revision of the Declaration of Helsinki. The study will also be carried out in keeping with local legal and regulatory requirements.

